Appendix 2 ITP Disease Activity - ITP-PAQ

ITP-PAQ®

This survey asks for your views about the impact of ITP on your health. Please check one box for each of the following questions.

	most of the time	some of the time	rarely	never
CONFIDENTIAL	▼	▼	▼	▼
1. In the past 4 weeks, how often did you have either bruising or petechiae (broken blood vessels)?				
2. In the past 4 weeks, how often did you have wounds or scars from blood tests, injections, or IV needles?				
3. In the past 4 weeks, how often did you have blood blisters in your mouth?				
4. In the past 4 weeks, how often did you have bleeding episodes (nose bleeds, gum bleeds, etc.)?				
5. In the past 4 weeks, how often did you have muscle aches ?				
6. In the past 4 weeks, how often did you have cramps in your legs ?				

ITP-PAQ v1.0 (05 September 2017)
US (English)

	all the time	most of the time	some of the time	rarely	never
7. In the past 4 weeks, how often did ITP or its treatments cause you to have difficulty falling asleep at bedtime?.....					
8. In the past 4 weeks, how often did ITP or its treatments cause you to awaken during the night ?.....					
9. In the past 4 weeks, how often did ITP or its treatments cause you to feel sleepy during the daytime ?.....					
10. In the past 4 weeks, how often did ITP or its treatments cause you to feel physically fatigued ?.....					

ITP-PAQ v1.0 (05 September 2017)
US (English)

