Secondary endpoint (Composite + hypothetical estimand)	Change from baseline in physical fatigue (Item 10 of the ITP-PAQ) in adults at Week 13 b	ITT	1) Rescue therapy (after 8 weeks of double-blind treatment): data after the initiation of rescue therapy will be imputed by the participant's worst post-baseline value on or before the use of rescue therapy, ie, worst observation carried forward, (for participants whose post-baseline values are all missing, the baseline value will be used to impute the missing Week 13 value) (composite strategy). 2) Discontinuation of study intervention before Week 13 due to lack of response or related adverse events: the same handling as 1) above (composite strategy). 3) Discontinuation of study intervention before Week 13 due to reasons other than the aforementioned: data during the double-blind on-treatment period up to Week 13 will be included in the analysis. Post-treatment data will be considered missing (hypothetical strategy).	Adults only: p-value, least squares mean difference and 95% CI from an analysis of covariance (ANCOVA) model with treatment group, randomization stratification factors d and geographic region as fixed effects, and baseline value as a covariate.  Missing data handling: A multiple imputation approach assuming missing at random will be used to impute missing Week 13 value, using all data during the double-blind on-treatment period up to Week 13 from participants who did not take rescue medication (after 8 weeks of double-blind treatment), nor discontinued before Week 13 due to related AE or lack of response. Note: before imputation (worst observation carried forward or multiple imputation), data will be set to missing for 4 weeks after the use of rescue therapy.

Endpoint Category (estimand)	Estimands			
	Endpoint a	Population	Intercurrent event(s) handling strategy	Population-level summary (Analysis and missing data handling)
Secondary endpoint (Composite + hypothetical estimand)	Change from baseline in IBLS assessment at Week 25 c	ITT	The same handling as for ITP-PAQ Item 10 above except that Week 25 will replace Week 13.	Adult population: p-value from ANCOVA with treatment group and randomization stratification factors d and geographic region as fixed effects and baseline value as a covariate.  Pediatrics: Descriptive.  The same handling of missing data as for ITP-PAQ Item 10 above except that Week 25 will replace Week 13.

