#### **3.3.1.2.4 Change from baseline on Item 10 of the ITP-PAQ (ie, physical fatigue) in adult participants ( $\geq 18$ years) at Week 13**

The analysis of this key secondary endpoint is to compare the change from baseline at Week 13 on Item 10 score of ITP-PAQ ([Section 3.7.3.2](#)) between the rilzabrutinib treatment group and the placebo treatment group in the adult ITT population via the primary estimand as defined in [Table 2](#).

Change from baseline in Item 10 score at Week 13 will be analyzed using an analysis of covariance (ANCOVA) model with the treatment group, randomization stratification factors and geographic region ([Section 3.1](#)) as fixed effects and baseline Item 10 score as a covariate. Missing score at Week 13 will be imputed via worst observation carried forward (WOCF) or multiple imputation as specified below which will result in multiple data sets of complete data. Each complete dataset will be analyzed by fitting an ANCOVA model. Statistical inference obtained from all imputed data will be combined using Rubin's rule (3). LS mean score changes in each treatment group, LS mean difference between treatment groups and their corresponding 95% CIs will be provided along with the p-value.

Observed Item 10 score at each visit and its change from baseline will be descriptively summarized. Cumulative distribution functions of Item 10 score in changes from baseline to Week 13 will be displayed by treatment groups. A shift summary from baseline to Week 13 and Week 25 will be provided for Item 10 raw score categorically.

**Intercurrent events** will be handled with a hybrid of composite and hypothetical strategy ([Table 2](#)). Specifically,

1. Rescue medication (after the initial 8 weeks of double-blind treatment): data after initiation of rescue therapy will be imputed by the participant's worst post-baseline value on or before the use of rescue therapy, ie, worst observation carried forward (for participants whose post-baseline values are all missing, the baseline value will be used to impute the missing Week 13 value) (composite strategy). For the purpose of worst observation carried forward, data will be set to missing for 4 weeks after the use of rescue therapy. In other words, only data more than 4 weeks after the use of rescue therapy will be carried forward.
2. Discontinuation of study intervention before Week 13 due to lack of response or related adverse events: the same handling as 1) above (composite strategy).

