3. Discontinuation of study intervention before Week 13 due to reasons other than the aforementioned: data at Week 13 during the double-blind on-treatment period will be included in the analysis. Post-treatment data will be considered missing (hypothetical strategy).

Note, per protocol the end of study visit is performed at 4-week post-dose follow up where participants will have their final assessment.

**Missing data** will be handled as followed,

- A multiple imputation approach will be used to impute missing Week 13 value, using all data during the double-blind on-treatment period up to Week 13 from participants who did not take rescue medication (after 8 weeks of double-blind treatment), nor discontinued before Week 13 due to related AE or lack of response, assuming missing at random and multivariate normal distribution. The imputation model will include treatment group, randomization stratification factors, geographic region ([Section 3.1](#)) as classified variables and baseline item score as a covariate. In case the baseline score is missing for a participant, the pooled mean of baseline score will be used.

Note: before multiple imputation, data will be set to missing for 4 weeks after the use of rescue therapy.

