#### 3.7.3.2 ITP Patient Assessment Questionnaire™ (ITP-PAQ™)

The ITP-PAQ (6, 7) is a disease-specific instrument designed to measure the QoL of adult participants with ITP. The instrument comprises 38 items completed by male respondents and 44 items completed by female respondents. Refer to [Section 5.5](#) for an example of the copyrighted scale.

The ITP-PAQ includes 10 scales,

- Symptoms (6 items, Items 1 to 6),
- Fatigue/Sleep (4 items, Items 7 to 10),
- Bother- Physical Health (3 items, Items 11 to 13),
- Activity (2 items, Items 14 to 15),

- Psychological Health (5 items, Items 16 to 20),
- Fear (5 items, Items 21 to 25),
- Overall QoL (5 items, Items 26 to 30),
- Social Activity (4 items, Items 31 to 34),
- Women's Reproductive Health (6 items, Items 35 to 40), and
- Work (4 items, Items 41 to 44)

The items employ a 4-week recall with responses recorded on 4- to 7-point Likert scales containing 4-7 responses. For example, five response options in a 5-point scale: 1 (never), 2 (rarely), 3 (some of the time), 4 (most of the time), 5 (all the time). The full list of 4- to 7-point scale scores could be found in [Section 5.5.3](#). All item scores are transformed to a 0 to 100 continuum where higher scores represent better QoL and are weighted equally to derive the scale scores.

- Each item score is transformed using the formula, transformed item score =  $100 * [(possible\ maximal\ item\ score - item\ score) / range]$ .
- The Women's Reproductive Health Scale will not be calculated for postmenopausal women.
- “Not applicable” will be treated as missing in Items 41 to 44.
- A scale score will be calculated by taking the average of transformed item scores within that scale if at least 50% of items for that scale are answered.

Each individual scale score and its change from baseline will be descriptively summarized at each visit. In addition, the change from baseline in the transformed score of Item 10 of the ITP-PAQ (i.e. physical fatigue) at Week 13 will be compared between the rilzabrutinib group and the placebo group ([Section 3.3.1.2.4](#)).

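### The 4-week blank after rescue does not clear Item 10's 4-week recall: Week 13 scores kept after rescue on Days 29 to 56 still recall 1 to 28 days of the window the SAP discards

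*SAP*

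**What the plan says.** Item 10 reads "In the past 4 weeks, how often did ITP or its treatments cause you to feel physically fatigued" (Protocol Appendix 2). SAP Section 3.7.3.2 confirms the period for the whole questionnaire: "The items employ a 4-week recall".

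Two rules in the SAP deal with rescue for this endpoint.

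- **Carry-forward.** The composite rule, which replaces later data with the participant's worst value, is limited to "Rescue medication (after the initial 8 weeks of double-blind treatment" (Section 3.3.1.2.4; Table 2 sets the same limit).
- **Blanking.** Table 2 adds that "before imputation (worst observation carried forward or multiple imputation), data will be set to missing for 4 weeks after the use of rescue therapy". Section 3.3.1.2.4 repeats this for the imputation step: "before multiple imputation, data will be set to missing for 4 weeks after the use of rescue therapy".

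Section 3.3.1.2.4 excludes from the imputation data only participants rescued after 8 weeks or discontinued before Week 13 for a related AE or lack of response. Someone rescued in the first 8 weeks therefore stays in, and keeps the observed Week 13 score once the blank has ended.

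**The concern.** The blank marks the 4 weeks after rescue as unusable. That works for a platelet count, which describes the day it is drawn. Item 10 looks back over a period as long as the blank, so a score taken the day after the blank ends can consist entirely of blanked days.

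The result is an abrupt change at Day 56. A participant rescued on Day 57 has later data replaced by the worst value. A participant rescued on Day 56 keeps an observed Week 13 score, treated as unaffected, whose whole recall lies in the discarded window.

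Item 10 at Week 13 belongs to the fixed-sequence, alpha-controlled family (Protocol Section 10.3.10; SAP Section 3.5). Rescue is itself a tested between-arm endpoint in that family, and SAP Section 3.3.1.2.3 plans a Kaplan-Meier estimate of rescue at Week 9. The plan thus allows for early rescue that differs between arms. What is at stake is whether the Week 13 score reflects assigned treatment, as the blanking rule intends, or partly reflects rescue.

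**Working it through.** **Inputs.** Item 10 recall is 28 days (Protocol Appendix 2; SAP 3.7.3.2). The blank is 28 days (SAP Table 2; 3.3.1.2.4). Carry-forward applies to rescue from Day 57 on (SAP 3.3.1.2.4). The target day is 1 + 7(n − 1) (SAP Table 12). The visit window is ±3 days (Protocol Table 1).

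**The plan's own figure.** Week 13 is 1 + 7 × 12 = Day 85, as in Table 12.

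**Rule.** Take rescue on Day d and a visit on Day V. The blank covers Days d to d + 28, so the score is kept if V > d + 28. The recall covers Days V − 28 to V − 1. Overlap is the number of days in both.

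**Week 13, V = 85.** The recall is Days 57 to 84.

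- The score is kept if d + 28 < 85, that is d ≤ 56.
- The discarded window reaches the recall if d + 28 ≥ 57, that is d ≥ 29.
- Overlap for d = 29 to 56 is (d + 28) − 57 + 1 = d − 28 days.

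| Rescue day | 29 | 35 | 42 | 49 | 56 |
|---|---|---|---|---|---|
| Recalled days inside the discarded window (of 28) | 1 | 7 | 14 | 21 | 28 |

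The mean over the 28 rescue days is (1 + 28)/2 = 14.5, or 14.5/28 = 52%. Overlap is 14 days or more for 15 of the 28 rescue days. If the blank is counted as d to d + 27, the overlaps are 0 to 27 with mean 13.5.

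**Visit window.**

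- V = 82 (recall Days 54 to 81): affected kept scores follow rescue on Days 26 to 53. Rescue on Days 54 to 56 is already blanked.
- V = 88 (recall Days 60 to 87): affected kept scores follow rescue on Days 32 to 56, with overlap of 1 to 25 days.

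The gap moves but does not close.

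**Week 9, V = 57.** The recall is Days 29 to 56. A score is kept if d ≤ 28, and the overlap is (d + 28) − 29 + 1 = d days, so 1 to 28 for rescue on Days 1 to 28. These scores feed the imputation model.

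**Effect of an 8-week blank.** A score is removed if V ≤ d + 56. At V = 85 that means d ≥ 29, so every affected Week 13 score is removed. Rescue on Days 1 to 28 leaves a kept score with no overlap.

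**How many participants.** The documents give no rescue rate for Days 29 to 56. Purely as an assumption, 5% to 20% of 194 adults would be 9.7 to 38.8, about 10 to 39 participants.

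**Other passages.** The supplementary repeated-measures analysis (3.3.1.3.3) states no rescue rule of its own. Step 2 of the Item 10 sample code (5.7.4) describes the imputed set as participants without rescue, with no 8-week limit, and the carry-forward set as those rescued after 8 weeks. Participants rescued by Day 56 appear in neither, whereas 3.3.1.2.4 keeps them in the imputation.

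**The case against.** **Leaving early rescue in the analysis is deliberate.** Table 2 names only rescue after 8 weeks as the rescue event for Item 10, and the primary endpoint uses the same cutoff. This stands as a reason to keep those participants. It does not explain the length of the blank: the Table 2 note applies to any rescue, and it discards 4 weeks without allowing for the recall.

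**The day limits are conditional.** They hold for a Day 85 visit and treat rescue as a single day. If the 4 weeks run from the end of a course, a course ending on Day 57 or later already blanks Day 85. This stands, and d should then be read as the last day of use.

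**The replacement is not neutral.** Newly blanked Week 13 scores would be imputed as missing at random from data that exclude participants rescued after 8 weeks or discontinued for a related AE or lack of response. Those who needed rescue on Days 29 to 56 may be imputed from people with a better course. This stands, and is why both rules should be reported.

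**The fix empties the imputation model.** This mostly fails. The existing rule already blanks Week 5 (Day 29) after rescue on Days 1 to 28 and Week 9 after rescue on Days 29 to 56. The change newly removes only Week 9 after rescue on Days 1 to 28 and Week 13 after rescue on Days 29 to 56.

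**The consequence is limited.** Item 10 is last of the five comparisons in Protocol Section 10.3.10, Table 2 marks it as not applicable to the EU and UK, and the Week 25 supplementary analysis (recall Days 141 to 168) is clear of rescue before Day 57. All true, but the confirmatory test is at Week 13.

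**Conclusion.** The defect is real and follows from the SAP's own rules: a 4-week blank cannot clear a 4-week recall. The day count rests on a Day 85 visit, rescue counted as one day, and the blank counted inclusively. No other passage repairs it.

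Two stronger readings are not supported.

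- A reader might infer that the kept Week 13 scores describe the rescue period itself. The overlap is partial, about half on average and only 1 day for rescue on Day 29. At a Day 85 visit the day of rescue never falls in the recall of a kept score.
- A reader might infer that rescue flatters placebo and shrinks the treatment difference. That needs both more rescue on placebo in those weeks and a fatigue benefit from rescue, and the documents give neither. The item asks about fatigue from ITP or its treatments, so rescue could move the score either way. Any figure in points would rest wholly on assumed rates and effects.

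The finding is a mismatch between the rule and the instrument in a confirmatory endpoint, with bias of unknown size and direction. It should be corrected.

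**What to change.** For Item 10, set a score to missing, before imputation or carry-forward, whenever its 4-week recall overlaps the 4 weeks after rescue, that is for 8 weeks from rescue in total. State whether the period runs from the first or the last day of use. Keep 4 weeks for platelet counts.

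Make the same change in Table 2 and in both places in Section 3.3.1.2.4 (the rescue rule and the note on missing data). Correct the Item 10 sample-code text in Section 5.7.4 so that it says where participants rescued in the first 8 weeks belong.

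Report the current 4-week rule alongside as a prespecified sensitivity analysis, because the newly blanked Week 13 scores depend on the missing-at-random model. Settle this before the adult data are unblinded.

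The cost is one rule and one programming constant, some further Week 9 and Week 13 scores blanked, and the Week 13 ones imputed. One narrow case needs noting: a participant rescued on Days 1 to 28 and again after 8 weeks could lose the only remaining post-baseline score, and carry-forward would then fall back on baseline, giving zero change.

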### 3.3.1.2.5 *Change from baseline in Idiopathic Thrombocytopenic Purpura Bleeding Scale (IBLS) assessment at Week 25 (applicable to countries within the EU (EEA countries) and UK only)*

The analysis of this key secondary endpoint is to compare the change from baseline at Week 25 on IBLS score ([Section 3.7.3.1](#)) between the rilzabrutinib treatment group and the placebo treatment group via the primary estimand as defined in [Table 2](#).

Change from baseline in IBLS score at Week 25 will be analyzed in the adult ITT population using the same analysis method as specified in [Section 3.3.1.2.4](#) for change from baseline in ITP-PAQ Item 10 except that Week 25 will replace Week 13.

For pediatric population, descriptive summary will be provided based on observed data.

**Intercurrent events and missing data** will be handled similarly as defined in [Section 3.3.1.2.4](#), except that Week 25 will replace Week 13.

Graphical presentations of the results will be provided as needed for the above secondary endpoints. Sample SAS® code could be found in [Section 5.7](#).

### 3.3.1.3 **Supplementary analysis I**

#### 3.3.1.3.1 *Number of weeks with platelet count $\geq 50,000/\mu\text{L}$ OR between $\geq 30,000/\mu\text{L}$ and $< 50,000/\mu\text{L}$ and at least doubled from baseline over the 24-week blinded treatment period in the absence of rescue therapy;*

*Number of weeks with platelet counts  $\geq 30,000/\mu\text{L}$  and at least doubled from baseline over the 24-week Blinded Treatment period in the absence of rescue therapy;*

*Time to first platelet count of  $\geq 50,000/\mu\text{L}$  OR between  $\geq 30,000/\mu\text{L}$  and  $< 50,000/\mu\text{L}$  and doubled from baseline during the 24-week Blinded Treatment period*

#### Alternative estimand regarding handling of intercurrent events

A sensitivity analysis will be performed using the same analysis method as the main analytical approach specified in [Section 3.3.1.2.1](#) or [Section 3.3.1.2.2](#) except that the intercurrent events will be handled as follows,

##### 1. Rescue medication:

- a) During the initial 8 weeks of double-blind treatment - *same handling as the primary estimand in [Section 3.3.1.2.1](#) or [Section 3.3.1.2.2](#).*
- b) After the initial 8 weeks of double-blind treatment: platelet counts after initiation of rescue therapy will be considered as no platelet response, ie, only the platelet counts up to the start date of rescue therapy will be included in analysis (composite strategy) - *more conservative handling than the primary estimand.*

2. Discontinuation of study intervention before Week 25.

- a) Due to related AE: platelet counts after the onset of AE will be considered as no platelet response, ie, only the platelet counts up to the onset of AE will be included in analysis (composite strategy) – *more conservative handling from the primary estimand*.
- b) Not due to related AE – *same handling as the primary estimand*.

**3.3.1.3.2 Proportion of participants requiring rescue therapy during the 24-week Blinded Treatment period**

Alternative estimand (analyzed via CMH)

Proportion of participants requiring rescue therapy during the 24-week Blinded Treatment period will be analyzed via CMH, the same analysis method as defined in the main analytical approach ([Section 3.2.2](#)) for the primary efficacy endpoint.

**3.3.1.3.3 Change from baseline on Item 10 of the ITP-PAQ (ie, physical fatigue) in adult participants (≥18 years) at Week 13**

Alternative estimand (analyzed via MMRM)

Change in Item 10 of the ITP-PAQ from baseline to Week 13, will be analyzed using a MMRM under the missing at random framework. The MMRM model will include treatment, randomization stratification factors and geographic region ([Section 3.1](#)), visit (Weeks 5, 9, 13), treatment-by-visit interaction as fixed effects, and baseline score-by-visit interaction as a covariate. The LS mean change for each treatment group, as well as the between-group LS mean difference and their associated 95% CI will be provided.

The MMRM model will be implemented using SAS® MIXED procedure with an unstructured correlation matrix to model the within-patient errors. Parameters will be estimated using the restricted maximum likelihood method with the Newton-Raphson algorithm. Denominator degree of freedom will be estimated using the Kenward-Roger approximation by fitting values from post-baseline scheduled visits.

**3.3.1.4 Supplementary analysis II**

**3.3.1.4.1 Change from baseline in Idiopathic Thrombocytopenic Purpura Bleeding Scale (IBLS) assessment at Week 13 (applicable to countries within the EU (EEA countries) and UK only)**

The same analyses as specified in [Section 3.3.1.2.5](#) will be performed similarly on change from baseline in IBLS score at Week 13.

#### 3.3.1.4.2 *Change from baseline in Item 10 of the ITP-PAQ (ie, physical fatigue) in adult participants ( $\geq 18$ years) at Week 25*

The same analyses as specified in [Section 3.3.1.2.4](#) will be performed similarly on change from baseline in Item 10 of the ITP-PAQ (ie, physical fatigue) in adult participants at Week 25.

### 3.3.2 Supportive secondary endpoint(s)

#### 3.3.2.1 *Other secondary endpoint – Stability of platelet response*

To qualify for a stable platelet responder (see endpoint definition in [Section 1.2.2.3.1](#)), a participant must have met ALL of the following criteria:

- Achieving initial platelet response, ie, platelet count  $\geq 50,000/\mu\text{L}$  within 12 weeks of initiation of rilzabrutinib [during double-blind period (protocol visit Week 2 to Week 13) for participants randomized to rilzabrutinib group, or during open-label period (protocol visit Week 26 to Week 37) for participants randomized to placebo group], and
- Following the initial platelet response, achieving platelet count  $\geq 50,000/\mu\text{L}$  for a period of 24 weeks, where
- There would be no 2 scheduled visits, at least 4 weeks apart, with a platelet count less than  $50,000/\mu\text{L}$ , without an intervening visit of platelet count  $\geq 50,000/\mu\text{L}$ . In other words, a participant would not be qualified for a stable responder if the participant has consecutive platelet counts  $< 50,000/\mu\text{L}$  for 4 weeks or longer (ie, from the first to the last occurrence of  $< 50,000/\mu\text{L}$  without any intervening visit of platelet count  $\geq 50,000/\mu\text{L}$ ) during this 24 weeks period after the initial response has been achieved. The participant's platelet counts within 4 weeks of rescue regimen will be considered as no response.
- Missing platelet count will be considered as no response.

The proportion of stable response will be calculated along with its 95% confidence interval (via normal approximation) in the open-label population ([Section 2](#)) as well as by randomized treatment group at the beginning of double-blind treatment, respectively.

For participants who are identified as a stable platelet responder, the duration of response will be descriptively summarized in the rilzabrutinib safety population ([Section 2](#)) as well as by randomized treatment group at the beginning of double-blind treatment, respectively. The duration of stable platelet response defined above is from the start date of stable platelet response up to

- The date of the first occurrence of 2 or more consecutive platelet counts  $< 50,000/\mu\text{L}$  for 4 weeks or longer (ie, when the stable response is lost), or
- 12 months after entering LTE,

whichever earlier.

